The two primary objectives of this study are to generate estimates, in particular variance estimates, for a sample size calculation of a subsequent fully powered RCT and to determine the likelihood of a successful conduct of such an RCT. The latter will be assessed by estimating recruitment and drop-out rate indication feasibility of a large-scale trial. Since this study is a pilot the statistical analysis will be primarily descriptive. Point estimates and corresponding 95% confidence intervals will be calculated for all outcome measures in the three arms and the aforementioned rates. Furthermore the distribution of outcome measures will be assessed to identify appropriate statistical analysis methods for a future RCT. Between group comparisons via statistical tests (unpaired two-sample t-test for continuous outcomes, Chi-squared tests for categorical (binary) outcomes) will be conducted, however, it will be clearly stated that these yield only preliminary results since the study is not powered for such investigations. The results of these tests will only be used to identify overwhelming evidence of inferiority of the two experimental treatments relative to usual care so that plans of a full trial can be abandoned or an arm dropped. In accordance with Kieser and Wassmer (1996), the upper 90% confidence limit will be chosen as the estimate of the variance of the treatment effect for a future trial's sample size calculation. Intention-to-treat and per protocol analyses will both be conducted to determine potential ranges of results.

References:

- 1. NICE. Guideline CG73 Chronic KIdney Disease.
- 3. System URD. USRD 2006 annual data report Bethesda, MD: National Institutes of Health, National Institute of Diabetes and Digestive and Kidney Diseases, 2006.

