- 3.Urea reduction rate of at least 65% during the three months before enrolment
- 4.Age 18 years or older

- 5. Able to complete the CPEX test and exercise training
- 6.Able to provide informed consent
- 7.Life expectancy of more than 6 months according to clinical assessment

Exclusion criteria:

- 1. Clinically significant valvular insufficiency
- 2. Clinically significant dysrythmia
- 3.Uncontrolled blood pressure: systolic > 160, diastolic >95 during the months before enrolment
- 4.Excessive fluid accumulation between dialysis sessions (>3 liters), more than twice pulmonary edema over 3 months before enrolment deemed to be due to excess fluid intake
- 5.Haemoglobin unstable and below 9.0
- 6.Ischemic cardiac event or intervention in the last 3 months
- 7. Morbidly obese, mid-thigh circumference of more than 60cm (EMS straps limit)
- 8. Clinically significant, still active inflammatory or malignant process
- 9.Pacemaker or cardiac device (contraindicated for bioelectrical impedance)
- 10.Patient highly physically active on their own accord.
- 11.Planned kidney transplant during study period.

Study design

This study is an open labeled, randomised controlled trial. Patients will be pre-screened using the clinical information available on their dialysis documentation. Eligible patients will be approached, patient information provided and then informed consent obtained. After randomisation patients will be allocated to one of the three study groups outlined in figure 1 below, with 12 weeks of dynamic exercise, LF-EMS or usual care.

[figure not shown]

Figure 1: Study flow diagram - R= randomization, W= washout effect, CPEX = cardiopulmonary exercise test, PWV = pulse wave velocity, FMD = flow mediated dilation, QOL = quality of life

Study flow: After patients have been approached and consented, the duration of their participation will be 20-24 weeks, undergoing 20 weeks study specific procedures.

Consenting (week -3 to-1): Eligible patients will be approached by the research nurse or the investigator and information provided. At the second visit, while on dialysis, the patients will be consented and all the potential procedures explained again. This will include a video explaining the two modalities of exercise, dynamic and LF-EMS.

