Baseline visit (week -1): This will coincide with a dialysis day and include obtaining clinical and QOL data, medication list, and a 'Sensewear' physical activity monitor armband will be fitted. 'Senswear' will allow validated measurement of free living physical activity over a 7 day period^{70, 71}.

Randomisation visit (week 0): This visit will occur on a non-dialysis day, during a short inter-dialytic interval and at least 12 hours after the last dialysis session. The visit will include an echocardiogram, bioelectrical impedance, CPEX with lung function test, applanation tonometry, flow mediated vascular dilatation, measurement of muscle strength and blood sampling for routine tests and for future testing of novel serum markers. Outcomes assessors will be blinded to the group allocation of the patient.

Participants will be randomised to one of 3 groups: 1) the intra-dialytic LF-EMS group, 2) the dynamic intra-dialytic exercise group or 3) the usual care without any dynamic exercise or LF-EMS group.

Treatment – familiarisation period (week 0-3): Exercise under close instruction and supervision will be commenced in patients randomised to either of the exercise groups. Over the initial 3 weeks, LF-EMS and dynamic exercise duration will be gradually increased to 30 mins per dialysis session. Previous work has indicated that 3 weeks of regular LF-EMS exposure is required to achieve an intensity that will elicit a cardiovascular training stimulus ⁷² (i.e. 40-60% VO₂ reserve⁷³). LF-EMS intensity will be gradually increased, as tolerated, with the aim of achieving the appropriate level by week 3. Dynamic exercise work load will be gradually increased to achieve a heart rate and workload equivalent to that achieved at 40-60% VO₂ reserve during baseline CPEX. As the use of heart rate during dialysis may not always provide an accurate reflection of workload⁷³, rating of perceived exertion (RPE) will also be used to monitor exercise intensity in both groups⁷².

Graded LF-EMS test (week 3): to ensure that LF-EMS tolerance has improved to a level that elicits a workload of 40-60% VO₂ reserve, a graded LF-EMS test will be performed in this group following the 3 week familiarisation period. This will be performed during a dialysis session. Stimulation intensity will be incrementally increased every 5 minutes until the tolerable level is achieved⁷² and oxygen consumption measured with the respiratory gas analysis system.

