Treatment visit (weeks 3-12): Patients in the exercise groups will progress from 30-45 mins of exercise at an intensity of 40-60% VO₂ reserve as regulated by heart rate and RPE. Where this isn't possible, maximal tolerated exercise intensity will be continued.

Treatment completion visit (week 13): This visit will occur on a non-dialysis day, during a short interdialytic interval and at least 12 hours after last dialysis session. The visit will include recording of any clinical events, QOL assessment, free living with 'Senswear' for the following 7 days, echocardiogram, bioelectrical impedance, CPEX with lung function test, applanation tonometry, flow mediated vascular dilatation, measurement of muscle strength and blood sampling for routine tests and for future testing of novel serum markers. Outcomes assessors will be blinded to the group allocation of the patient.

Exercise training and EMS in kidney disease Page 7 of 17 Version 1 - 07.11.2013

Wash out and study completion visit (week 20): This part of the study will only be performed, if further funding can be obtained. This visit will occur on a non-dialysis day, during a short inter-dialytic interval and at least 12 hours after last dialysis session. The visit will include recording of any clinical events, QOL assessment and free living physical activity with 'Senswear' for the following 7 days, echocardiogram, bioelectrical impedance, CPEX with lung function test, applanation tonometry, flow mediated vascular dilatation, measurement of muscle strength and blood sampling for routine tests and for future testing of novel serum markers. During the 8 week 'washout' period, patients will undertake usual care which will not involve dynamic exercise training or LF-EMS.

Randomisation: Stratified permuted block randomisation with a variable block size (sizes 3 and 6 used) will be employed. Stratification variables are age (young, middle-aged, old) and gender (male, female), and a separate permuted block randomisation will be performed within each of the six strata. The randomisation list will be created and held by a Warwick Medical School statistician who the study team are going to contact to obtain the group allocation of a recruited patient. The randomisation list will not be made available to the study team.

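### The protocol gives the team of an open-label three-arm trial its block sizes (3 and 6), the smaller equal to the number of arms, which weakens allocation concealment

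*Protocol*

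**What the plan says.** The Randomisation paragraph of the Protocol sets the scheme: "Stratified permuted block randomisation with a variable block size (sizes 3 and 6 used) will be employed". It continues: "Stratification variables are age (young, middle-aged, old) and gender (male, female". No ages are attached to the three age bands. Each combination has its own list: "a separate permuted block randomisation will be performed within each of the six strata". The proportion of blocks of each size is not given.

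The same paragraph protects the list. A medical school statistician creates and holds it, and is the person "who the study team are going to contact to obtain the group allocation of a recruited patient". It ends: "The randomisation list will not be made available to the study team".

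Under Study design: "This study is an open labeled, randomised controlled trial". The randomisation visit and the treatment completion visit both carry the safeguard "Outcomes assessors will be blinded to the group allocation of the patient". Consent is taken one to three weeks before the week 0 randomisation.

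The sample size paragraph gives 30 patients per group. Outcome measures makes tolerability, safety, acceptance, adherence and quality of life (QOL) the primary outcome, compared across arms. Statistical analyses describes a mainly descriptive pilot. Its between-group tests serve only to detect overwhelming inferiority to usual care, on which an arm or the full trial could be dropped.

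**The concern.** Keeping the list away from the team stops anyone reading the next assignment. It does not stop anyone working it out. In an open-label trial the team knows what each earlier patient received, and the Protocol supplies the other thing needed for deduction, the set of possible block lengths. With three arms a block of 3 is the shortest possible, so balance returns quickly and the arm used least so far is often the next one.

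If staff can anticipate the next arm, they can change which patient is randomised next or when. Fitter or keener patients could then collect in the exercise arms. That would distort between-arm comparisons of tolerability, dropout and QOL. Blinded outcome assessment does not correct this, because the selection happens before allocation, and QOL is reported by patients who know their arm.

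**Working it through.** **Inputs.** From the Protocol: block sizes 3 and 6, three arms, six separate lists, 30 patients per group. Equal allocation is inferred from the equal group sizes and from block sizes that are multiples of 3. The total is 3 × 30 = 90, an average of 90 / 6 = 15 per stratum. Assumed, because not stated: each block is equally likely to be a 3 or a 6 (range 25% to 75% size 3), and the strata are of equal size. The guesser is assumed to know every earlier allocation in the stratum but not the length of the current block. The Protocol states no predictability figure to reproduce.

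**Method by hand, first three patients of a stratum.** In a block of size B with k = B/3 places per arm, the chance that the next patient gets arm a is (k − number already given a) / (places left). The two sizes are weighted by their posterior probability.

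- Patient 1: each arm 1/3.
- Patient 2, after A. In a block of 3: A 0, B and C 1/2 each. In a block of 6: A 1/5, B and C 2/5 each. Mixed: A = 0.5 × 0 + 0.5 × 0.2 = 0.10; B = C = 0.5 × 0.5 + 0.5 × 0.4 = 0.45.
- Patient 3, after A then B. The posterior for a block of 3 is 0.5 / (0.5 + 0.4) = 0.556. P(C) = 0.556 × 1 + 0.444 × 0.5 = 0.78.
- Patient 3, after A then A. Only a block of 6 allows this, so A is ruled out and B and C have 1/2 each. If B and B follow, both remaining places must be C, and the next two allocations are known.

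The last line shows what publishing the sizes adds: knowing that no block exceeds 6 turns a tendency into a certainty.

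**Simulation over whole strata**, same rule, optimal guesser, 15 patients per stratum:

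| Sizes | Best guess correct | Next arm certain | At least one arm ruled out |
|---|---|---|---|
| 3 and 6, 50:50 | 57% | 8% | 20% |
| 3 and 6, 75% size 3 | 59% | 4.5% | 12% |
| 3 and 6, 25% size 3 | 55% | 9.7% | 25% |
| 6, 9 and 12, equal mix | 50% | 2% | 6% |

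Chance is 33%. The ruled-out column includes the certain cases. With the 50:50 mix, 8% of 90 is about 7 patients. The best guess has at least 60% probability for about 39% of patients. Unequal strata of 4 to 34 patients give 55.8% correct and 7.1% certain.

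**What drives the 57%.**

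- *Number of lists.* One unstratified list of 90 gives about 57.6% correct and 8.6% certain, slightly more than six lists of 15.
- *Knowledge of the stratum.* A simple guesser picks the arm used least so far. Knowing the stratum, that guesser is right about 57% of the time; following gender only, 47.7%; with no stratum information, 43.4%.
- *Knowledge of the sizes.* The simple guesser makes no use of the block sizes and still reaches about 57%. Small blocks produce the guess rate; disclosure adds the certain and ruled-out deductions.

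**The case against.** The strongest reply is that the scheme already has the main safeguards. An outside statistician holds the list, each allocation is released for a recruited patient, consent comes before randomisation, block size varies, and assessors are blinded. The figures assume perfect tracking by stratum across five sites, and site is not a stratum. The trial is a pilot whose stated objectives are variance estimates and feasibility. The recruitment target and the 20% dropout limit are study-wide, so steering between arms would affect them little. Every entrant must be able to exercise, which narrows the scope for steering by fitness.

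Most of this stands as a limit on size. The figures are upper bounds and no bias in any outcome has been estimated. It does not remove the point. A held list does not prevent deduction from visible allocations, consent in advance does not fix the order in which consented patients are randomised, and one study team obtains every allocation. Between-arm comparisons are still planned and can lead to an arm being dropped.

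A reader might infer more than the document supports:

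- *That six lists or vague age bands make prediction easier.* They do not. One list is slightly more predictable, and staff who cannot place a patient in a band guess worse.
- *That allocation is usually known in advance.* It is certain for only about 8% of patients.
- *That one person both chooses whom to approach and calls for the allocation.* The Protocol names the research nurse or the investigator for the approach and only the study team for the call.
- *That hiding the sizes would cure the problem.* It leaves the 57%.

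**Conclusion.** The concern holds in a limited form. By stating block sizes of 3 and 6 to an open-label team, the Protocol partly undoes the concealment that it sets up in the same paragraph. As an upper bound, a diligent tracker guesses the next arm correctly about 57% of the time instead of 33%, knows it for about 8% of patients (4-10% across mixes of 25-75% size-3 blocks), and can exclude at least one arm for about 20%. This rests on the assumed mix, on about 15 patients per stratum and on full knowledge of earlier allocations.

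The weakness bears on the between-arm comparisons of tolerability, dropout and QOL, and hardly at all on overall recruitment or overall dropout. It is worth correcting because the correction is cheap; the document gives no evidence that allocation would in fact be subverted. The missing age cut-points are a separate, minor gap in specification: the Protocol fixes neither the bands nor who assigns them, so the list for a borderline patient is left to judgement.

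**What to change.** 1. Remove the block sizes from the Protocol. State only that permuted blocks of varying size are used, and keep the sizes in the statistician's restricted randomisation file. This costs nothing. It removes the certain and ruled-out deductions but does not lower the 57%.
2. Have the statistician generate the list from larger undisclosed sizes. With 6, 9 and 12 as an example, correct guesses fall to about 50%, certain predictions to about 2% and ruled-out arms to about 6%, even if the sizes became known. The price is slightly more possible imbalance from incomplete blocks: the largest gap between two arms within a stratum is B/3, so 12/3 = 4 instead of 6/3 = 2. With about 15 patients per stratum that is a real but modest trade-off. The change is cleanest before the first patient is enrolled; after that it can apply only to allocations not yet made.
3. Separately, fix numeric age cut-points before the first patient and have the statistician assign the stratum from date of birth, so that it is not open to discretion. This is a wording change.

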- 1.Intra-dialytic exercise training is well tolerated and improves well-being in stable, chronic dialysis patients.
- 2.Intra-dialytic exercise training significantly improves cardiovascular and skeletal muscle function with reversal of the catabolic process.
- 3. The effect of intra-dialytic LF-EMS exercise on cardiovascular and skeletal muscle function and its tolerability is comparable to dynamic exercise training effects.

Aims are:

- 1.To assess the tolerability of intra-dialytic dynamic exercise and LF-EMS interventions compared to conventional treatment without exercise intervention in patients on regular dialysis for end stage renal failure.
- 2.To assess the improvement of quality of life with intra-dialytic dynamic exercise and LF-EMS interventions compared to conventional treatment without exercise intervention in patients on regular dialysis for end stage renal failure.
- 3.To evaluate the effects of intra-dialytic dynamic exercise training compared to conventional treatment without exercise intervention on measures of functional cardiovascular and skeletal muscle function.
- 4.To evaluate the effects of LF-EMS intra-dialytic exercise training compared to conventional treatment without exercise intervention on measures of functional cardiovascular and skeletal muscle function.
- 5.To qualitatively compare the effects of LF-EMS with dynamic intra-dialytic exercise training on measures of functional cardiovascular and skeletal muscle function.

Participants:

Patients on chronic and stable haemodialysis, under the renal care of Nephrologists at the University Hospital Coventry and Warwickshire NHS Trust will be invited to take part and will be randomised after informed consent is received.

Haemodialysis sites: Patients from five different sites under the care of the Nephrologists at the UHCW will be approached. At these sites, 450 patients are receiving regular dialysis.

- 1. University Hospital, Coventry, UHCW NHS Trust; Dialysis Unit
- 2.Rugby St. Cross Hospital, UHCW NHS Trust; Ash Dialysis Unit
- 3. The Whitnash Satellite Renal Unit; UHCW NHS Trust
- 4. Stratford Hospital, Stratford upon Avon, UHCW NHS Trust, Dialysis Unit
- 5.George Elliot Hospital NHS Trust, Nuneaton; Lucy Dean Dialysis Unit

Inclusion criteria: Participants will need to fulfill following criteria for enrolment in one of the three arms of the study:

- 1.On haemodialysis for at least 3months
- 2.On 3 times 4 hours of dialysis per week

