Sample size calculation: Since this is a pilot study, no formal sample size calculation was conducted. The sample size was chosen based on Kieser and Wassmer (1996), who recommended recruiting 20 to 25 patients per group for a pilot study (with a normally distributed outcome) where the aim is to minimise the overall sample size of pilot and large scale RCT. Being conservative, a drop-out rate of 20% is assumed and thus a sample size of 30 patients per group has been chosen.

Dynamic exercise and electrical muscle stimulation treatment intervention

Low frequency electrical stimulation (LF-EMS) (treatment group): Bilateral neoprene straps will be applied to the quadriceps and hamstrings 3 times per week during the second hour of dialysis. Rhythmical contractions will occur at a frequency of 3-4 Hz. Participants will be introduced to the EMS protocol very gradually to ensure tolerance and adherence. On the first occasion the straps will be activated for 5 minutes at a very light current amplitude (milliamps, mA) (less than visible contraction), so that participants can become accustomed to the unusual sensation. During the following 8 familiarisation sessions (3 weeks), duration will be incrementally increased to 30 mins and intensity increased as tolerated. By the end of the third week the intention is that the patient will be accustomed to using the straps for 30 mins at an intensity equivalent to 40-60% VO2 reserve⁷². This will be assessed with an intradialytic graded LF-EMS CPEX (as above). During LF-EMS sessions, exercise intensity will be regulated using a combination of heart rate and rating of perceived exertion (RPE). Intensity will be further increased over the 9 week period of the intervention to the maximum tolerated level. This is necessary to ensure that, whilst cardiovascular reserve and skeletal muscle function improve, intensity remains at a level that will elicit a cardiovascular exercise response. Duration will also be increased to 45 mins by the second week of the intervention and will remain at this level throughout. Each session will be preceded by a 10 minute 'ramp-up' period during which intensity will be gradually increased to the training level⁷². Each session will be concluded with a 5 minute cool-down at a gradually reducing intensity. The LF-EMS units will record the intensity and duration of the stimulation which can be downloaded for analysis.

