Study aim 3: Effects of intra-dialytic dynamic exercise training compared to conventional treatment without exercise intervention on measures of functional cardiovascular and skeletal muscle function.

Study aim 4: Effects of LF-EMS intra-dialytic exercise training compared to conventional treatment without exercise intervention on measures of functional cardiovascular and skeletal muscle function.

Study aim 5: Qualitatively compare the effects of LF-EMS with dynamic intra-dialytic exercise training on measures of functional cardiovascular and skeletal muscle function.

Outcome measures

The **primary outcome** measure is the tolerability, safety and acceptance of LF-EMS, compliance/ adherence to LF-EMS and improvement of QOL measures with LF-EMS in comparison to dynamic exercise and a conventional treatment approach.

The **secondary outcome** measures are cardiovascular and skeletal muscle improvement with LF-EMS in comparison to dynamic exercise and a conventional treatment approach.

Qualitative

Acceptance and tolerability: This will be assessed by recruitment rate into the study (target = 20% of the available population recruited (i.e. 90 out of 450) and recruitment targets met in the specified timescale of 18 months), willingness of participants to be randomised to LF-EMS, dynamic exercise or control; tolerance to the two interventions and compliance/adherence to the protocol (no more than 20% study dropout; reasons will be recorded).

Quality of life (QoL): Health related quality of life will be assessed using the Kidney Disease Quality of Life (KDQOL-36TM) questionnaire which has been extensively validated in CKD populations^{74, 75}. In addition, the Kansas City Cardiomyopathy Questionnaire will be administered which has been validated for use in stable and decompensated heart failure populations⁷⁶.

Nutritional status: To provide a global assessment of nutritional status, the Malnutrition-Inflammation Score⁷⁷ will be calculated following assessment by a renal dietitian, within 20 minutes of completion of a dialysis session. This tool is a validated measure of nutritional status in ESRD and is predictive of mortality in haemodialysis patients^{78, 79}.

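### The 20% recruitment target is the planned sample divided by every dialysis patient at the five units, so reaching it does not estimate acceptance

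*Protocol*

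**What the plan says.** All references are to the Protocol, the only document at hand.

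- **Outcome measures, Acceptance and tolerability.** Acceptance is assessed by a recruitment rate: "target = 20% of the available population recruited (i.e. 90 out of 450"). The same sentence requires recruitment to be complete within 18 months. It also lists willingness to be randomised, tolerance of the two interventions, and a study dropout of no more than 20%. Acceptance is named in the primary outcome.
- **Haemodialysis sites.** The denominator is the unit census: "At these sites, 450 patients are receiving regular dialysis".
- **Randomisation visit and Sample size calculation.** "Participants will be randomised to one of 3 groups", and "thus a sample size of 30 patients per group has been chosen".
- **Study design.** "Patients will be pre-screened using the clinical information available on their dialysis documentation". Eligible patients are then approached and asked for consent.
- **Statistical analyses.** One of the two primary objectives is to judge whether a full trial could be carried out: "The latter will be assessed by estimating recruitment and drop-out rate indication feasibility of a large-scale trial". Point estimates with 95% confidence intervals are planned for these rates.

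**The concern.** A recruitment rate that stands for acceptance should have in its denominator the people who could have accepted or refused. Here the denominator is everyone on dialysis at the five units. Seven inclusion and eleven exclusion criteria then apply, and only those who pass are approached. One inclusion criterion is being able to complete the exercise test and the training, while the background section on LF-EMS says that dynamic exercise is commonly out of reach in end-stage renal disease. A patient who was never asked is counted in the same way as one who refused.

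The numerator target is the planned sample itself, so the threshold coincides with full enrolment. A planner of the full trial who reads 20% could not tell whether the criteria were restrictive or the patients unwilling. These are different problems with different remedies, and the pilot exists to inform that decision.

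**Working it through.** **Inputs.** Groups: 3 (Randomisation visit). Patients per group: 30 (Sample size calculation). Census: 450 (Haemodialysis sites). Recruitment period: 18 months (Acceptance and tolerability). Criteria: 7 inclusion + 11 exclusion = 18. The eligible share of the 450 is not given and is assumed below.

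**1. Reproducing the target.** 3 × 30 = 90, and 90/450 = 0.200. The stated 20% is reproduced exactly.

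**2. Where the 90 comes from.** The sample size section cites a source "who recommended recruiting 20 to 25 patients per group for a pilot study" and states that "a drop-out rate of 20% is assumed". For 24 patients, 24/(1 − 0.2) = 30. For 25 patients, 25 × 1.2 = 30, or 25/(1 − 0.2) = 31.25, rounded up to 32. The 30 per group thus rests on a pilot-size rule plus dropout. No expected level of willingness enters it, so the 20% target contains none either.

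**3. What 20% says about uptake.** Let E be the number eligible and R the number recruited. Then R/450 = (E/450) × (R/E): the reported rate is eligible share times uptake. With R = 90:

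| Assumed eligible share | E | Uptake among eligible, 90/E | Reported rate |
|---|---|---|---|
| 100% | 450 | 20% | 20% |
| 80% | 360 | 25% | 20% |
| 60% | 270 | 33% | 20% |
| 40% | 180 | 50% | 20% |
| 30% | 135 | 67% | 20% |
| 20% | 90 | 100% | 20% |

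The 450 is also a count at one time. Patients can become eligible during the 18 months, for instance by reaching the required 3 months on haemodialysis. They could enter the numerator without being in the denominator.

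**4. The ceiling.** If enrolment ends at the planned 90, the proportion cannot exceed 20%. It reads 20% whether the 90 are enrolled in 9, 12 or 18 months, that is at 90/9 = 10, 90/12 = 7.5 or 90/18 = 5 per month.

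**5. Below the ceiling.** A shortfall is visible. With exact 95% intervals, 45 recruits give 45/450 = 10.0% (7.4% to 13.2%) and 75 give 75/450 = 16.7% (13.3% to 20.4%).

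**6. The interval at the target.** The exact binomial 95% interval for 90/450 is 16.4% to 24.0%. It assumes that the count of 90 could have varied freely. If enrolment ended because 90 was reached, the count was set by the plan and the time taken was the random quantity.

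**7. The speed target.** 90/18 = 5.0 per month, with an exact Poisson 95% interval of 4.0 to 6.1. Over five units this is 1.0 per unit per month. This quantity still varies when the sample is filled, because the time to fill it varies.

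**The case against.** A reader might infer that the criterion measures nothing, that it cannot inform recruitment to a full trial, or that the planned confidence interval is meaningless. The Protocol does not support these readings.

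- A target equal to the planned sample is a one-sided feasibility threshold, and it detects failure (step 5). This stands.
- The same sentence sets an 18-month limit, which gives a speed of 5 per month that does bear on a full trial. This stands.
- Recruits per head of census is a coarse figure that could be carried to other units of known size. This stands in part: it assumes similar eligibility and willingness there, and it understates potential if the sample fills early.
- The Protocol never says that enrolment stops at 90, nor that the interval is to be computed on 90/450. A monthly rate would fit the wording of Statistical analyses. The point about the interval is therefore conditional.
- Willingness to be randomised is listed separately. That is so, but it has no denominator or threshold, and it is worded for participants, so it is unclear whether refusals among approached patients are counted.
- Tabulating screening counts is often left to an analysis plan or a flow diagram. That would answer a complaint of omission. Here the Protocol itself fixes the denominator and the target, and the choice is a poor one for the quantity it is meant to represent.

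**Conclusion.** The point holds in a limited form. The 20% target is the planned sample over all prevalent dialysis patients, not over those eligible or approached. Reaching it shows that the planned sample was filled. It does not estimate acceptance, because any uptake among eligible patients from 20% to 100% is compatible with it. That range, and the narrower 25% to 67% for eligible shares of 80% to 30%, rest on assumed shares. They show how ambiguous the figure is, not an error of known size.

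The criterion keeps value as a sign of shortfall and, through the 18-month limit, as a measure of speed. The reservation about a binomial interval applies only if enrolment ends at 90 and the interval is taken on 90/450. The matter should be corrected because acceptance is part of the primary outcome and recruitment is one of the two rates on which feasibility of the full trial is judged. It does not undermine the randomised comparison.

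**What to change.** In Outcome measures, Acceptance and tolerability:

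1. Define acceptance as the number who consent divided by the number eligible and approached.
2. Report, each with a 95% confidence interval: eligible/screened, approached/eligible, consented/approached and randomised/consented. Include patients who become eligible during the 18 months.
3. Keep 90 patients in 18 months as a recruitment-speed target only, reported as randomised patients per unit per month with a confidence interval.

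The counts can come from a log of the pre-screening and approach that Study design and Study flow already plan, with reasons for ineligibility and refusal. The cost is the small work of keeping that log and a change of wording. The log should run from the first patient screened, since refusals that are not recorded at the time may not be recoverable.
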